8.1 Name and Description of the Method of Investigation

The investigational treatment the CE marked FreeStyle Libre 2 (FSL2) flash glucose monitoring device (Abbott Diabetes Care, Oxon, UK).

8.2 Intended Purpose

The intended purpose of the investigational treatment is flash-glucose monitoring intended at replacing finger-stick glucose levels.

8.3 Method of Administration

The FSL2 glucose sensor is directly attached to the patient. Each sensor is intended to last for 14 days. The component not directly attached to the patient is the handheld reader and/or mobile phone app which display current and historical glucose data (Figure).

8.4 Required Training

Prior to commencement of the study, the research team nurses/clinicians at each of the investigation centres will be trained to use the FSL2 system and its components. This will be documented on each site's training log. Prior to the use of study devices, participants will be trained to use the FSL2..

8.5 Precautions

During treatment with insulin there is a risk of hypoglycaemia and hyperglycaemia. Participants will be educated in minimising this risk during the study.

8.6 Accountability of the Method under Investigation

The local Investigator will provide training for the study participants and will make every effort, through regular contact, to ascertain study is conducted according to protocol. Devices will be identified using batch/lot/serial numbers and the location of investigational devices and their dates of use by participants will be documented throughout the study.

9 Study Schedule

9.1 Overview

The study will be co-ordinated from Manchester Clinical Trials Unit and performed at following sites:

1. Diabetes Centres within Manchester University Foundation Trust
2. Diabetes Centres within University Hospitals of Derby and Burton NHS Foundation Trust
3. University Hospitals Birmingham NHS Foundation Trust
4. Addenbrookes Hospital, Cambridge
5. Norfolk and Norwich University Hospital, Norwich
6. Queen Alexandra Hospital, Portsmouth
7. Ipswich Hospital, East Suffolk and North Essex NHS Foundation Trust, Ipswich
8. Wareham Surgery (Wareham) and The Adam Practice (Poole), NHS England Primary Care GP Practices

After recruitment, consent, participants will be randomised for 24-weeks home use of flash-glucose monitoring or 24-weeks use finger-stick glucose monitoring.

The study includes up to 7 visits for participants completing the study. Maximum time in study is 30 weeks. Each study visit can be scheduled with +/- 2 weeks of the planned visit date.

Study visits will be conducted through virtual consultation supported by video conferencing and telephone (when appropriate) or if available at individual sites through face to face clinics or a mixture of both. For those who choose to enter the trial by virtual means, any required devices, study documents and kits for HbA1c collections will be provided to participants free of charge with pre-paid return postage. All study visits conducted remotely will use Video/ Audio consultation tools approved by the local NHS organisation.

Table 1 outlines study activities when participant is randomised to flash glucose monitoring intervention (intervention group).

Table 2 outlines study activities when participant is randomised to finger-stick glucose monitoring (control group).

Table 1. Schedule of study visits when participant is randomised to flash glucose monitoring intervention (intervention group). All study visits could be done remotely.

Visit/ contact	Description	Time since randomisation	Start relative to previous / next Visit / Activity**	Duration
Visit 1	Recruitment & Screening visit: Consent HbA1c, baseline bloods, questionnaires	-2 to -3 weeks	-	2 hours
Visit 2	Blinded flash glucose monitor insertion	-2 weeks	Within 1 to 2 weeks of Visit 1. Can coincide with Visit 1	0.5 hour
Visit 3	Adherence assessment & Randomisation Flash-glucose monitoring initiation - Training, education & competency assessment	0 weeks	After 2 weeks of Visit 2	2 hours
Visit 4	Review data /optimisation and use of study devices. Data download & collect participant diary	+4 weeks	After 4 weeks of Visit 3	1 hour
Visit 5	Review data /optimisation. Data download - HbA1c. - Collect participant diary	+12 weeks	After 8 weeks of Visit 4	2 hours
Visit 6	Not applicable in this arm			
Visit 7	End of Flash-glucose monitoring intervention arm - HbA1c - Questionnaires - Data download - Collect participant diary	+24 weeks	12 weeks after Visit 5	2 hours

**Each study visit can be scheduled with +/- 2 weeks of the planned visit date.

Table 2. **Schedule of study visits when participant is randomised self-monitoring of blood glucose**
All study visits could be done remotely.

Visit/ contact	Description	Time since randomisation	Start relative to previous / next Visit / Activity**	Duration
Visit 1	Recruitment & Screening visit: Consent HbA1c, baseline bloods, questionnaires	-2 to -3 weeks	-	2 hours
Visit 2	Blinded flash glucose monitor insertion	-2 weeks	Within 1 to 2 weeks of Visit 1. Can coincide with Visit 1	0.5 hour
Visit 3	Adherence assessment & Randomisation Self- monitoring of glucose initiation - Education	0 weeks	After 2 weeks of Visit 2	2 hours
Visit 4	Review data /optimisation Collect participant diary	+4 weeks	After 4 weeks of Visit 3	1 hour
Visit 5	Review data /optimisation. Data download - HbA1c - Collect participant diary	+12 weeks	After 8 weeks of Visit 5	2 hour
Visit 6	Blinded flash glucose monitor insertion (Extra visit in this arm)	+22 weeks	After 10 weeks of Visit 5	
Visit 7	End of self-monitoring intervention arm - HbA1c. - Questionnaires - Collect participant diary	+24 weeks	2 weeks after Visit 6	2 hour

**Each study visit can be scheduled with +/- 2 weeks of the planned visit date.

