	during a remote video consultation supported by online education material developed by Diabetes Technology Network. Participants will be advised to use flash glucose monitoring continuously for the next 24 weeks.
2. Self-monitoring of blood glucose	Masked FSL2 will be applied for two weeks, during the last two weeks of control period. Education will focus on using finger-stick measurement for treatment optimisation with education provided either in person or during a remote video consultation supported by online educational material such as Bertie Online(www.bertieonline.org.uk). Blinded FSL2 will be posted to participants where necessary for self-insertion with relevant advice.
End of 24 week assessments	
 - A blood sample will be taken for measurement of HbA1c using the local laboratory (face to face clinic) or a home HbA1c where the participant will collect a blood sample using a self-test kit and send in a pre-paid envelope to a central or third party external laboratory. - Validated questionnaires as described before evaluating quality of life, mood, needle burden, disordered eating, diabetes distress and diabetes treatment satisfaction will be completed either during face to face clinics or by postal delivery for virtual consultations. 
Additional questionnaire for those in the FSL2 arm exploring expectations and experience of using FSL2 during the study will also be administered.

Procedures for safety monitoring during trial	Standard operating procedures for reporting all adverse events will be in place.

3 Summary

FreeStyle Libre 2 (FSL2) is a novel glucose monitoring device (Flash glucose) in the form of a disc worn on the arm for 14 days and a hand-held reader which is designed to largely replace the recommended 4-10 painful finger-stick blood glucose tests required each day for the self-management of type1diabetes. The purpose of this study is to determine whether flash glucose monitoring with FSL2 device will improve HbA1c over a 24-week period compared to self-monitoring of blood glucose in adults and adolescents (16 years or older) with sub-optimally controlled (HbA1c 7.5% to 11%) type 1 diabetes.

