9.8 Visit 7: (+24 weeks since randomisation): End of randomised study treatment

The participant will be invited to attend the research centre approximately 12 weeks after Visit 5. This would be the end of 24 weeks randomised study period. All study devices will be downloaded.

Insulin usage data will be recorded and diaries collected. The participant will have a blood test for the HbA1c. Body weight measurement will be made where possible. Participant will be asked to complete questionnaires evaluating diabetes related quality of life, diabetes distress and diabetes treatment satisfaction. In addition, participants in the FSL2 arm will be asked to complete a questionnaire exploring expectations and experience of using FSL2 during the study. For those participants who have completed the trial by virtual means, any remaining devices, completed study documents and blood collections for HbA1c testing can be returned free of charge with pre-paid return postage.

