#### 3.2 Adherence and protocol deviations

##### 3.2.1 Adherence

During Visit 3, participant's adherence / tolerance of using the flash-CGM over the preceding 14 days will be assessed. To proceed with the study participant should have worn the blinded glucose monitoring device for at least 10 days during last 14 days of run-in period. If the participant fails to demonstrate adherence or develops any significant allergy or intolerance to the glucose sensor, the participant will be removed from the study.

The number and percentage of participants failing to demonstrate adherence and not wearing the blinded glucose monitoring device for at least 10 days will be presented in a table.

During the trial, intervention adherence data will be collected and analysed as part of the process evaluation and will also be considered in a sensitivity analysis of the primary outcome measure using Complier Adjusted Causal Estimation (see Section 5.2.3). During Visit 7, participant's adherence / tolerance at the control group of using the flash-CGM over the preceding 14 days will also be assessed. Participants' adherence will be defined as wearing the blinded glucose monitoring device for at least 10 days during last 14 days of Visit 7. The number and percentage of participants at the control group failing to demonstrate adherence and not wearing the blinded glucose monitoring device for at least 10 days will be presented in a table. The percentage of time wearing the glucose sensor alongside mean glucose sensor usage will also be recorded for participants in the flash-glucose monitoring arm.

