#### Sensor-based

The respective sensor-based measures obtained during the last 2 weeks of the 24-week randomised interventions contrasting the flash-glucose against the SMBG will be compared

using ANCOVA. Analysis will be adjusted for baseline sensor values obtained during blinded run-in period, the baseline HbA1c and the other variables included in the minimisation allocation algorithm. Analysis will also be repeated for day and night-time period (the interval from 7.00 to 23:00 defines day-time period; 23:00 to 07:00 am defines the night-time period).

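### A ±2-week window on the two-week Visit 6 to Visit 7 interval lets a fully compliant control fail the SAP's 10-of-14-day wear rule and mistimes the control arm's sensor data

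*Protocol*

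**What the plan says.** **Schedule.** Protocol 9.1, Table 2 (repeated in SAP 2.7) puts the control arm's extra visit for blinded sensor insertion at +22 weeks. Visit 7 is at +24 weeks and, in the adjacent column, "2 weeks after Visit 6". The footnote to both visit tables reads "Each study visit can be scheduled with +/- 2 weeks of the planned visit date". Its marker sits on the column that times each visit relative to the one before. Protocol 9.8 is also loose about the final visit: "The participant will be invited to attend the research centre approximately 12 weeks after Visit 5".

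**Sensor.** Protocol 8.3 states "Each sensor is intended to last for 14 days". The synopsis gives the intention for controls: "Masked FSL2 will be applied for two weeks, during the last two weeks of control period".

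**Analysis.** SAP 3.2.1 sets the control-arm wear rule: "Participants' adherence will be defined as wearing the blinded glucose monitoring device for at least 10 days during last 14 days of Visit 7". Failures are only to be tabulated, as counts and percentages. SAP 5.2.2 takes as its data "The respective sensor-based measures obtained during the last 2 weeks of the 24-week randomised interventions", compared between arms by ANCOVA.

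**The concern.** The synopsis and the SAP both assume that the control sensor is worn in the fortnight that ends at the final visit. The schedule does not secure this, because Visit 7 may move by as much as the whole interval that separates it from Visit 6. Someone who wears the sensor for all 14 days and attends both visits in window can still miss the SAP's rule because of booking dates alone.

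Every sensor-based secondary outcome (overall, daytime and night-time) and the sensor part of the safety objective (time below 3.0 mmol/l) depend on this one sensor in controls. FSL2 participants are advised to wear sensors continuously, so a continuing user has the last 14 days whenever Visit 7 falls. Any mistiming or shortfall from this source therefore arises in one arm only.

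The documents contain no safeguard aimed at it:
- The repeat-sensor rule for under 10 days of data (Protocol 9.4) is written for the run-in only.
- These visits are in window, so the SAP 3.2.2 deviation category for visits outside the window does not catch them.
- The visit-window sensitivity analysis in SAP 5.2.3 concerns primary outcome data.
- Secondary outcomes are analysed on complete cases (SAP 5.3).

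**Working it through.** **Inputs.** Visit 6 at +22 weeks, Visit 7 at +24 weeks and a window of ±14 days (Protocol 9.1; SAP 2.7); sensor life of 14 days (Protocol 8.3); at least 10 worn days in the last 14 (SAP 3.2.1). I read the last as the 14 days ending at Visit 7, and take the sensor to start on the day of Visit 6.

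**The plan's own interval.** 24 - 22 = 2 weeks = 14 days, as Table 2 states.

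**Permitted gap g from Visit 6 to Visit 7.**
- Counted from the actual Visit 6 date, as the footnote marker suggests: g = 14 ± 14, so 0 to 28 days. Visit 7's window alone produces this range.
- Both visits counted from randomisation: Visit 6 falls on days 140 to 168 (weeks 20 to 24) and Visit 7 on days 154 to 182 (weeks 22 to 26). The minimum is 154 - 168 = -14 and the maximum is 182 - 140 = 42 days. The visits may coincide or even come in the wrong order.

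**Days of the last 14 that one sensor can cover with perfect wear.**

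cover(g) = max(0, min(14, g) - max(0, g - 14))

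This is g for gaps of 0 to 14, 28 - g for gaps above 14 and up to 28, and 0 otherwise.

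| Gap (days) | 0 | 7 | 9 | 10 | 14 | 18 | 19 | 21 | 28 |
|---|---|---|---|---|---|---|---|---|---|
| Days covered | 0 | 7 | 9 | 10 | 14 | 10 | 9 | 7 | 0 |

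**Meeting the rule.** cover(g) ≥ 10 requires g ≥ 10 and 28 - g ≥ 10, so 10 ≤ g ≤ 18. The rule tolerates 14 ± 4 days and the schedule allows 14 ± 14. On the first reading, 9 of the 29 whole-day gaps can satisfy the rule and 20 cannot. On the second, with the visits in order (0 to 42 days), 9 of 43 can and 34 cannot. These are counts of permitted dates, not predicted shares of participants.

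**What happens to the data.**
- Gap of 7 days: if recording stops when devices are downloaded at Visit 7 (Protocol 9.8), the record is 7 days long. On the postal route in Protocol 9.7, the sensor is worn for two weeks and then returned, so the record can be complete with 14 - 7 = 7 of its days after Visit 7.
- Gap of 21 days: the record is complete but ended 21 - 14 = 7 days before Visit 7.

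SAP 5.2.2 does not say whether its last two weeks are the calendar fortnight to week 24, the 14 days before Visit 7, or the 14 days after insertion. It therefore does not settle which of these days are analysed.

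**The case against.** The strongest reply is that the consequences are small. Table 2 plans a 14-day gap, sites will generally book to it, and at 14 days the rule is met with 4 days to spare on either side. Failing the rule leads only to a line in a table: no passage removes the participant from the sensor analyses or sets a minimum number of days. On the postal route a short gap shifts the record and does not truncate it, and with self-insertion the wear dates need not follow the visit dates at all. SAP 5.2.3 also leaves room for further sensitivity analyses, including on key secondary outcomes. No direction of bias is shown, and the primary outcome does not use the sensor.

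Most of this stands, and it limits what may be claimed. It does not remove the mismatch: the schedule permits gaps at which the SAP's rule cannot be met, and the discretionary sensitivity analyses neither redefine the rule nor fix the analysis period.

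Two stronger readings are tempting. A reader might infer that, because the footnote marker sits on the relative-timing column, the windows accumulate and Visit 7 could drift to 24 ± 6 weeks (FSL2 arm, three links) or 24 ± 8 weeks (control arm, four links). Protocol 9.1 caps time in the study at 30 weeks and Protocol 9.4 requires at least 10 days of run-in sensor data, so Visit 7 cannot fall later than about 30 - 10/7 = 28.6 weeks after randomisation. The tables and the headings of 9.7 and 9.8 also time these visits from randomisation. A reader might also infer a definite loss of control participants and wider standard errors. That needs an exclusion rule and a distribution of visit dates, and the documents give neither.

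**Conclusion.** The point holds as an inconsistency between the visit window and the SAP's wear rule, on either reading of the planned visit date. In-window gaps run from 0 to 28 days (or -14 to +42), and only gaps of 10 to 18 days allow the rule to be met with one 14-day sensor. A fully compliant control can thus be reported as non-adherent. Control sensor data can fall outside the intended last two weeks, or be short where recording ends at the Visit 7 download, while a continuing FSL2 user is not exposed to this.

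The conclusion assumes one sensor, started at Visit 6 and lasting its stated 14 days. How many participants would be affected, and at what cost in precision, cannot be derived from the documents. The primary HbA1c analysis is untouched. The change is worth making because the whole control side of the sensor comparison rests on this one wear period and the correction is cheap.

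**What to change.** 1. **SAP.** In 3.2.1, count control-arm worn days over the 14 days from the Visit 6 sensor start. In 5.2.2, define the control arm's sensor analysis period in the same way. This removes the mislabelling and settles which days are analysed.
2. **Protocol.** In the Table 2 footnote and in 9.7 and 9.8, replace the independent ±2 weeks on Visit 6 with insertion 14 days before the booked Visit 7. Keep Visit 7 within 24 ± 2 weeks of randomisation in both arms. Aim to hold it about 14 days after sensor start, without moving it outside that window, so that the primary-outcome visit does not wait on a secondary measure.

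The schedule repeated in SAP 2.7 should be brought into line. The cost is a few lines of text and slightly less freedom in booking Visits 6 and 7 in the control arm; no extra visit or sensor is needed.

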9.2 Visit 1: Recruitment Visit and Screening Assessment

Once the participants have agreed to participate in the study, they will be invited for the recruitment visit, and given a participant ID, when the following activities will be performed by the research team: Due to the current COVID-19 pandemic all study visits can be provided by virtual consultation supported by video conferencing and telephone (when appropriate).

- written informed consent/assent (Signed consent form can be returned to the research team with pre-paid postage for those following the virtual pathway).
- checking inclusion and exclusion criteria
- medical and diabetes history including presence of diabetes complications and hypoglycaemia burden
- ethnicity, body weight and height measurement; calculation of BMI
- Demographic data (Date of Birth, Gender registered at birth, Full Postcode)
- record of current insulin therapy
- record of occupation and educational attainment
- any history of disordered eating or needle phobia
- previous participation in structured education, status of carb counting, use of bolus calculator

9.2.1 Screening Blood Sampling

Blood samples will be taken to measure HbA1c. This will be done using a local laboratory (face to face clinic) or a home HbA1c where the participant will collect a blood sample using a self-test kit and send in a pre-paid envelope to a central or third party external laboratory. . Less than 15 ml of whole blood will be taken from each participant.

9.2.2 Questionnaires at Screening

Evaluation of participants' responses in terms of quality of life, diabetes distress, needle burden, disordered eating, depression and diabetes treatment satisfaction using EQ-5DL-5L questionnaire, Type 1 Diabetes Distress Scale (DDS), Diabetes fear of injecting and self-testing (D-FISQ) questionnaire, Diabetes Eating Problem Survey (DEPS-R), Diabetes Treatment Satisfaction Questionnaire (DTSQ), Patient Health Questionnaire (PHQ-9) and The Glucose Monitoring Satisfaction Survey (GMSS). Hypoglycaemia burden will be assessed using Clarke questionnaire and Gold score. Where necessary questionnaires will be provided by postal delivery for participants who choose to join the virtual pathway.

9.3 Visit 2: Insertion of blinded glucose monitoring device

Purpose of visit 2 is to insert a blinded glucose monitor (FreeStyle Libre Pro device). Participant will be provided with instructions about using this device for next 2 weeks. Visit 2 may be combined with visit 1. Eligible participants who join the trial by virtual consultation will receive a Blinded FSL2 pro sensor and reader by post for self-insertion with relevant advice. At the end of the two weeks the participant can return the items to the research team by pre-paid postal services.

9.4 Visit 3: Adherence assessment, randomisation and start of study treatment

During Visit 3, participant's adherence / tolerance of using the flash-CGM over preceding 14 days will be assessed. To proceed with the study participant should have worn the blinded glucose monitoring device for at least 10 days' during last 14 days of run-in period. If the participant fails to demonstrate adherence or develops any significant allergy or intolerance to the glucose sensor, the study will be terminated and participant will be removed from the study. If the sensor records less than 10 days' worth of data due to a problem with the sensor itself (premature sensor failure) rather than a participant related issue, a new sensor should be inserted to get a minimum of total 10 days' worth of data. In cases in which there is a premature sensor failure, participant randomisation should only proceed once a minimum total of 10 days data has been downloaded. Participants who are opting for virtual consultations and who have <10 days data, will be provided with a new FSL2 pro sensor and reader to obtain the minimum data requirements prior to randomisation.

9.4.1 Randomisation scheme

Randomisation to one of the two intervention arms (24-weeks use of flash-glucose monitoring or 24 weeks use of conventional finger-stick glucose monitoring) will use the minimisation method, with a random element to improve allocation concealment. We will minimise over the following factors: study centre (Birmingham; Cambridge; Derby; Manchester; Norwich; Portsmouth), baseline HbA1c (7.5%-9.0%; >9.0%-11%), treatment modality (Multiple daily injections (MDI); Continuous Subcutaneous insulin Infusion (CSII)), prior participation in structured education course (yes; no) and current use of bolus calculator (yes; no).

